## **2.4. Randomization and Blinding**

This is a non-randomized, open-label study and there is no blinding.

## **2.5. Sample Size and Power Considerations**

As this is an open-label extension study, no sample size calculations have been performed. Patients who completed the HART or the PRIDE-HD study and met patient exclusion/inclusion criteria will be enrolled.

## **2.6. Sequence of Planned Analyses**

### **2.6.1. Planned Interim Analyses**

There will be no formal interim analysis for this study.

### **2.6.2. Final Analyses and Reporting**

All analyses identified in this SAP will be performed after the end of study as defined in the study protocol.

This SAP and any corresponding amendments will be approved before database lock, in accordance to SOP GBP\_RD\_702 (Statistical Analysis Plan).

### **3. ANALYSIS SETS**

#### **3.1.1. Intent-to-Treat Analysis Set**

The intent-to-treat (ITT) analysis set will include all enrolled patients, regardless of whether or not a patient took any study drug.

#### **3.1.2. Safety Analysis Set**

The safety analysis set will include all patients who receive at least 1 dose of study drug.

#### **3.1.3. Full Analysis Set**

The full analysis set will include all patients in the ITT analysis set who receive at least 1 dose of study drug and have a baseline and at least 1 post-baseline UHDRS-TMS assessment.

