At **Visit 1 (1 Month)** the following will be documented: an evaluation for research study consent, review of concomitant medications (including inquiry about changes in use of benzodiazepines and antidepressants); inquiry about changes in use of alcohol and illicit drugs, AEs, C-SSRS, PBA-s, vital signs and drug compliance. Evaluation for Research Study Consent, ECG and blood draw (calcium, magnesium, potassium, and creatinine for creatinine clearance calculation) will be performed for patients from the PRIDE-HD study.

Subsequently, the patient will be contacted every 3 months as per below:

At **Telephone or in-person Visits [Safety Visit (SV)] (eg after 3, 9, 15 months etc.)** the following will be documented: an evaluation for research study consent, review of concomitant medication (including inquiry about changes in use of benzodiazepines and antidepressants); inquiry about changes in use of alcohol and illicit drugs, C-SSRS and PBA-s assessment, review of AEs, and assessment of compliance with trial medication. A 12-lead ECG will be obtained, vital signs will be assessed and calcium, magnesium and potassium level and creatinine for

creatinine clearance calculation will be drawn [hypokalemia is defined as a potassium level less than 3.5 mEq/L]. If less than 3.5 mEq/L, patient's study drug will be suspended until normal (greater than or equal to 3.5mEq/L). Participants can choose to have the assessments of vital signs, ECG and blood draw for calcium, magnesium, potassium, and creatinine for creatinine clearance calculation performed by their GP and/or local cardiologist or schedule a visit with site but the site must have a telephone contact with the participant to review concomitant medication, AEs and assess compliance with trial medication.

At **Telephone contacts [C] (eg once a month between on-site visits)** the following will be documented: an evaluation for research study consent, review of concomitant medication (including inquiry about changes in use of benzodiazepines and antidepressants); inquiry about changes in use of alcohol and illicit drugs, review of adverse events, C-SSRS and an abbreviated PBA-s assessment.

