At **Clinic Visits (eg 6, 12, 18 months etc.)** the following tests will be performed and documented: an evaluation for research study consent, brief physical examination including vital signs and weight, calcium, magnesium, and potassium levels and creatinine for creatinine clearance calculation will be drawn [hypokalemia is defined as a potassium level less than 3.5 mEq/L]. If less than 3.5 mEq/L, patient's study drug will be suspended until normal (greater than or equal to 3.5mEq/L), review of concomitant medication (including inquiry about changes in use of benzodiazepines and antidepressants); inquiry about changes in use of alcohol and illicit drugs, review of AEs, C-SSRS, PBA-s, 12-lead ECG and assessment of compliance with trial medication. On a yearly basis, UHDRS (including motor assessment, cognitive assessment, behavioral assessment, functional capacity, independence scale, functional Assessment) and a pregnancy test (for females of childbearing potential) should be done. The PBA-s will be collected at all safety and clinic visits except on those at which the UHDRS is performed.

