## **2.2. Efficacy Measures**

- Unified Huntington's Disease Rating Scale – Total Motor Score (UHDRS-TMS)
- Unified Huntington's Disease Rating Scale – Total Functional Capacity (UHDRS-TFC)
- Unified Huntington's Disease Rating Scale – Functional Assessment (UHDRS-FA)
- Unified Huntington's Disease Rating Scale – Independence Scale (UHDRS-IS)
- UHDRS Behavioral Assessment
- UHDRS Cognitive Assessment
- PBA-s (also part of safety measures)

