## **6. EFFICACY ANALYSIS**

### **6.1. General**

The full analysis set analysis set will be used for all study population summaries unless otherwise noted. Summaries will be presented for all patients.

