### **6.2. Efficacy Endpoint and Analysis**

The efficacy endpoints are as follows:

- UHDRS-TMS change from baseline to each visit that this is measured.
- UHDRS-TFC change from baseline to each visit that this is measured.
- UHDRS-FA change from baseline to each visit that this is measured.
- UHDRS-IS change from baseline to each visit that this is measured.
- UHDRS Behavioral total score change from baseline to each visit that this is measured.
- UHDRS Cognitive tests change from baseline to each visit that this is measured.
- PBA-s total score change from baseline to each visit that this is measured.

All efficacy endpoints will be summarized for actual values and changes from baseline to each visit using descriptive statistics.

UHDRS Behavioral domain scores and the PBA-s domain scores will also be summarized for actual values and changes from baseline of this study to each visit using descriptive statistics.

No formal inferential statistics will be applied to the efficacy endpoints. Efficacy analyses will be considered exploratory.

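### Every planned PBA-s summary omits treated patients who leave before Month 12 without a post-baseline motor score

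*SAP*

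**What the plan says.** - **The set.** SAP 3.1.3 takes patients from the ITT set who had at least one dose and who "have a baseline and at least 1 post-baseline UHDRS-TMS assessment".
- **Its use.** SAP 6.1, in the efficacy section: "The full analysis set analysis set will be used for all study population summaries unless otherwise noted". SAP 6.2 lists seven efficacy endpoints, one of them "PBA-s total score change from baseline to each visit that this is measured", and notes no exception for any of them.
- **UHDRS timing.** It is done at baseline. After that, SAP 2.1 under Clinic Visits has: "On a yearly basis, UHDRS (including motor assessment, cognitive assessment, behavioral assessment, functional capacity, independence scale, functional Assessment".
- **PBA-s timing.** SAP 2.1 lists for the Month 1 visit "AEs, C-SSRS, PBA-s, vital signs and drug compliance". For later visits it says: "The PBA-s will be collected at all safety and clinic visits except on those at which the UHDRS is performed". Safety visits fall at Months 3, 9, 15 and so on, clinic visits at Months 6, 12, 18 and so on. The abbreviated form is used at the Week 1 call, at the monthly telephone contacts and at the call one month after stopping drug.
- **Dual role.** SAP 2.2 has the entry "PBA-s (also part of safety measures", and SAP 2.3 names the PBA-s beside the C-SSRS under suicidality. SAP Section 7, which uses the safety analysis set, plans C-SSRS summaries (7.8) and none for the PBA-s.
- **Withdrawal and unscheduled data.** SAP 4.5 uses both: early termination data go to the next scheduled visit, unscheduled data to the corresponding one.

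**The concern.** Membership of the set depends on one instrument, the motor examination, whose first scheduled repeat comes a year after baseline. The PBA-s is collected mainly in the gaps between UHDRS visits. A patient can therefore supply months of PBA-s data and still be left out of every PBA-s table because a different assessment was never repeated.

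This would be a small matter for an efficacy measure alone. But the SAP also calls the PBA-s a suicidality measure, and no safety table picks it up. A measure listed as safety is then reported only for patients who stayed to about Month 12 or came back for an examination. Those missing would be mainly patients who died, were lost to follow-up or withdrew consent early. A summary of the first nine months should not depend on what happened to the patient afterwards.

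**Working it through.** The plan states no sample size, power or dropout figure, so there is nothing to reproduce. The check follows one patient through the rules and then shows how the size depends on quantities that the documents do not give.

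**1. First qualifying TMS.** Yearly UHDRS after baseline (SAP 2.1) puts the first scheduled post-baseline TMS at Month 12. Before that, only a TMS at an early termination or unscheduled visit can qualify a patient (SAP 4.5).

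**2. PBA-s occasions before Month 12 (SAP 2.1).**
- Named as PBA-s without qualification: Months 1, 3, 6 and 9, so 4 visits.
- Abbreviated form: Week 1, plus monthly calls at Months 2, 4, 5, 7, 8, 10 and 11 if one call is made in each month without a visit: 1 + 7 = up to 8 contacts.

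**3. Which of these give a total score.** SAP 4.4 allows up to 25% of items to be missing: 0.25 × 11 = 2.75, so at most 2 of 11. The abbreviated form, as the protocol describes it (Sections 1.3 and 4.7.3), has 6 items. That leaves 5/11 = 45% missing, so it never yields a total. The totals at stake are those from the 4 visits, taking the unqualified term to mean the full form. From the calls, only item or domain scores could be lost.

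**4. Example.** A patient leaves at Month 8 with no TMS after baseline. PBA-s was due at Months 1, 3 and 6. Visits used under SAP 3.1.3: 0. Visits used if the set required only a post-dose PBA-s value: 3. For someone leaving just before Month 12 the comparison is 0 against 4.

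**5. The other endpoints.** TFC, FA, IS, behavioral and cognitive scores belong to the same UHDRS, done at the same visits as the TMS. A patient with no post-baseline UHDRS has no change score on any of them, whatever the set definition. Little beyond baseline values is lost there.

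**6. Size.** Let d be the share leaving before Month 12 and w the share of those with no post-baseline TMS. The share excluded is d × w. Neither input is in the documents, so both are assumed:
- lowest: 0.05 × 0.10 = 0.5%
- middle: 0.20 × 0.25 = 5%
- highest: 0.30 × 1.00 = 30%

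The width of this range shows that the documents do not fix the size.

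**The case against.** The strongest reply is that few patients may be affected. SAP 2.1 calls for a clinic visit on withdrawal, and SAP 4.5 uses its data. Protocol Amendment 05 schedules the UHDRS at end of treatment, early termination and, as needed, unscheduled visits, and its Section 7.7.2 asks for a full evaluation at discontinuation. Patients who stop drug for safety or tolerability may also stay on the visit schedule and reach Month 12. This stands in part. The SAP follows Amendment 04 and says that Amendment 05 was not implemented. Its own withdrawal text does not mention the UHDRS, and the schedule it defers to (protocol 1.2) is not in the text available. Patients who die or are lost have no withdrawal visit in any case.

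A second reply is that a TMS-based set is reasonable, because the primary objective includes UHDRS development and one fixed population keeps tables comparable. That is fair for the UHDRS endpoints. It gives no reason to gate the PBA-s.

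Third, suicidality is not lost from the report: C-SSRS and adverse events are summarised for all treated patients. That limits the harm but does not replace the PBA-s.

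Several stronger readings are tempting but not supported:
- *All efficacy data of early leavers are lost.* Only the PBA-s has scheduled values before Month 12 that the rule discards.
- *One unscorable motor examination removes a patient.* SAP 4.4 prorates with up to 7 of 31 assessments missing (0.25 × 31 = 7.75), one post-baseline TMS at any time suffices, and SAP 3.1.3 speaks of an assessment, not a non-missing total.
- *The summaries favour patients who do better.* Selection on retention follows from the rule; its direction is not shown.
- *A count out of 47 patients.* That number comes from the unimplemented Amendment 05 and is not shown to be the number at risk in year 1.
- *An undeclared departure from the protocol.* The efficacy set in protocol 8.2 is not tied to the TMS, but that is Amendment 05 wording; the Amendment 04 text is not shown.

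**Conclusion.** The point holds in a narrow form. As written, the SAP leaves out of every planned PBA-s summary any treated patient who leaves before Month 12 with no TMS at a withdrawal or unscheduled visit. Up to four PBA-s visits per such patient go unused, plus any item or domain scores from up to eight abbreviated contacts. The UHDRS endpoints are little affected.

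How many patients this concerns is unknown; the 0.5% to 30% range rests wholly on assumed dropout and assumed missing examinations. The visit counts assume monthly calls and the full form at Months 1, 3, 6 and 9. Because SAP 6.2 is descriptive and exploratory, no error rate or power is involved. The consequence is an avoidable selection in early PBA-s results. This is a minor but cheap improvement.

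**What to change.** Add one sentence to SAP 6.1/6.2 or 7.8: PBA-s total, domain and suicidality item scores will be summarised by visit in the safety analysis set, using all treated patients with at least one post-dose PBA-s value.

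Alternatively, redefine the full analysis set endpoint by endpoint, requiring at least one post-baseline value of the endpoint being summarised. For the PBA-s, do not also require a baseline value: the Baseline Visit in SAP 2.1 lists no PBA-s, so such a condition could empty the table. What the change-from-baseline PBA-s endpoint then means is a separate question that concerns all patients, whichever set is used.

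The cost is one sentence, agreed before database lock, and an n that varies slightly between tables. SAP 4.1 already reports n, so the variation will be visible.

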## **4. GENERAL ISSUES FOR DATA ANALYSIS**

### **4.1. General**

Descriptive statistics for continuous variables include n, mean, standard deviation (SD), standard error (SE), median, minimum, and maximum. Descriptive statistics for categorical variables include patient counts and percentages, missing category will be displayed as appropriate.

### **4.2. Specification of Baseline Values**

The baseline value is the last observed data prior to the first dose of study drug in this study.

### **4.3. Scoring for Rating Scales**

A detailed description for all rating scales below can be found in the protocol.

The UHDRS comprises a broad assessment of features associated with HD. It is a research tool which has been developed to provide a uniform assessment of the clinical features and course of HD. The TMS component of UHDRS comprises 31 assessments from the 15 items of the UHDRS. The UHDRS-TMS is calculated as the sum of the 31 motor assessments.

The TFC scale of the UHDRS assesses 5 functional domains associated with disability (occupation, finances, domestic chores, activities of daily living, and care level). The UHDRS-TFC is calculated as the sum of the 5 functional capacity items.

The FA component of the UHDRS assesses 25 items associated with functional problems. The UHDRS-FA is calculated as the sum of the 25 items.

The behavioral assessment of the UHDRS comprises 11 items that measures the frequency and severity of symptoms related to affect, thought content and coping styles. Severity and frequency scores are multiplied (after setting all values outside the range of 0-4 to missing) to produce an overall score for each item. The total behavioral score is the sum of the overall scores across the 11 items.

The PBA-s is a brief semi-structured interview covering the most common behavioral and psychiatric manifestations of HD. The interview is not restricted to a single construct, but rather covers several broad symptom domains relevant to HD, comprising 11 items. Each symptom is rated for severity and for frequency. Severity and frequency scores are multiplied (after setting all values outside the range of 0-4 to missing) to produce an overall 'PBA score' for each symptom. The PBA total score is the sum of all PBA scores across the 11 symptoms.

### **4.4. Handling Withdrawals and Missing Data**

For all variables, only the observed data from the patients will be used in the statistical analyses, ie, there is no plan to estimate missing data.

For the TMS component of the UHDRS, if responses to 1 assessment up to 25% of assessments are missing, the missing responses will be replaced by the average of the remaining responses within the TMS component. If responses to more than 25% of the assessments are missing, the missing responses will not be replaced and the UHDRS-TMS will be set to missing.

For the TFC scale of the UHDRS, if responses to 1 item up to 25% of items are missing, the missing responses will be replaced by the average of the remaining responses within the TFC scale. If responses to more than 25% of the assessments are missing, the missing responses will not be replaced and the UHDRS-TFC will be set to missing.

For the FA component of the UHDRS, if responses to 1 assessment up to 25% of assessments are missing, the missing responses will be replaced by the average of the remaining responses within the FA component. If responses to more than 25% of the assessments are missing, the missing responses will not be replaced and the UHDRS-FA will be set to missing.

For the behavioral assessment of the UHDRS and the PBA-s, the severity x frequency items need to be calculated before calculating the total score. If either the severity or frequency value is missing then the item will be equal to the nonmissing value. After calculating the items, if responses to 1 item up to 25% of items are missing, the missing responses will be replaced by the average of the remaining responses. If responses to more than 25% of the items are missing, the missing responses will not be replaced and the total score will be set to missing.

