#### **4.7.1.2 Function**

The functional assessment battery of the UHDRS will be administered. The functional assessment scale assesses 25 items associated with functional problems ([Huntington Study Group, 1996](#)).

This scale assesses 5 functional domains associated with disability (occupation, domestic chores, activities of daily living, care level). Individual domain scores range from 2 or 3 (fully functional) to 0 (severely disable), with a total of 13 points possible ([Huntington Study Group, 1996](#)).

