#### **4.7.3 Problem Behaviors Assessment – Short Form**

Because of the prominence of psychiatric symptoms in HD, it is recommended that the PBA-s form be used in all HD studies with any need for behavioral assessment as a comprehensive screen for the most common psychiatric symptoms in HD (Craufurd et al 2001; Kingma et al 2008). The PBA-s is a brief semi-structured interview covering the most common behavioral and psychiatric manifestations of HD. The interview is not restricted to a single construct, but rather covers several broad symptom domains relevant to HD, comprising 11 items: low mood, suicidal ideation, anxiety, irritability, anger/aggressive behavior, loss of motivation, perseverative thinking or behavior, obsessive-compulsive behaviors, paranoid thinking, hallucinations, behavior suggestive of disorientation. Each symptom is rated for severity on a 5-point scale according to detailed scoring criteria, which roughly correspond to the following: 0 = "not at all"; 1 = trivial; 2 = mild; 3 = moderate (disrupting everyday activities) and 4 = severe or intolerable. Each symptom is also scored for frequency on a 5-point scale as follows: 0 = symptom absent; 1 = less than once weekly; 2 = at least once a week; 3 = most days (up to and including some part of everyday); and 4 = all day, every day. Severity and frequency scores are multiplied to produce an overall 'PBA score' for each symptom.

Only the abbreviated PBA-s (i.e. items of the PBA-s relevant to suicidality [depressed mood, suicidal ideation, anxiety, irritability, loss of motivation, obsessive-compulsive behaviors]) will be collected during the TCs and virtual visits when the UHDRS is not completed. If the patient has a positive score 1 and 2 on the suicidal ideation item or depressed mood item of the PBA-s, the patient will be monitored more closely and treated according to the investigator's (or qualified designee's) medical judgment. Patients with C-SSRS or PBA-s suicidality scores 1 and 2 may be handled by investigator (or qualified designee)/neurologist with a consultancy with psychiatrist(s) where necessary per investigator's (or qualified designee's) medical judgement.

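### Two scoring rules in SAP 4.4 misstate totals: a half-missing behavioural or PBA-s item takes the lowest value a present symptom can have, and mean replacement of a TFC item ignores unequal item maxima

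*SAP*

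**What the plan says.** **Behavioural assessment and PBA-s.** SAP 4.3 scores each item as severity times frequency, "after setting all values outside the range of 0-4 to missing", and sums 11 items for each total. Protocol 4.7.3 also makes the PBA-s item a product: "Severity and frequency scores are multiplied to produce an overall" item score. It anchors frequency as "0 = symptom absent; 1 = less than once weekly; 2 = at least once a week", rising to 4; severity 1 is the trivial level. When one half of an item is absent, SAP 4.4 says: "If either the severity or frequency value is missing then the item will be equal to the nonmissing value". Only after that step does it apply the 25% limit: up to a quarter of items may be replaced by the mean of the rest, and beyond that the total is missing.

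**TFC.** SAP 4.3: "The UHDRS-TFC is calculated as the sum of the 5 functional capacity items". Protocol 4.7.1.2: "Individual domain scores range from 2 or 3 (fully functional) to 0 (severely disable), with a total of 13 points possible". If one item is absent, SAP 4.4 says "the missing responses will be replaced by the average of the remaining responses within the TFC scale". Nothing rescales for the different item maxima or caps the total.

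**Use.** SAP 6.2 lists the TFC, the behavioural total and the PBA-s total as efficacy endpoints, for example "PBA-s total score change from baseline to each visit that this is measured".

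**The concern.** Setting a product to one of its factors amounts to setting the other factor to 1. That is not neutral. On the PBA-s anchors it asserts that the symptom occurs less often than weekly, or is trivial. The item is then treated as complete, so the limit meant to stop totals resting on too little data is bypassed. SAP 4.3 can itself create such items, since an out-of-range severity or frequency becomes missing.

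For the TFC, a plain mean is safe only if all items share one range. That is true of the motor assessments, all rated 0 to 4, but not of the TFC.

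Collecting UHDRS information is part of the primary objective, and these scores are reported as values and as change. A half lost at follow-up lowers the change (an apparent behavioural improvement); a half lost at baseline raises it. The TFC moves up or down according to which item was lost. Behavioural and PBA-s domain scores are summarised too, and one wrong item is diluted less there than in an 11-item total.

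**Working it through.** **Inputs.** Severity and frequency each run 0–4, with 11 items (SAP 4.3). The 25% limit is in SAP 4.4. The TFC has 5 items (SAP 4.3), with item maxima of 2 or 3 and a total of 13 (protocol 4.7.1.2).

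**Half-missing items**

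1. Let *s* be the observed half and *f* the true value of the missing half. The true item is *s × f*; the SAP gives *s*. The shortfall is 1 − 1/*f*: 0%, 50%, 67% and 75% for *f* = 1, 2, 3, 4. With *s* = 4 the possible products for a present symptom are 4, 8, 12 and 16, and the SAP always gives 4.
2. Of the 16 pairs with both halves 1–4, the SAP value is right in 4 (*f* = 1) and too low in 12. Equal weights on the pairs, for illustration only, give a mean of 2.5 under the rule against a true mean of 2.5 × 2.5 = 6.25.
3. Limit: 0.25 × 11 = 2.75, so at most 2 of 11 items may be replaced. Half-missing items are not counted towards this.
4. Example: a stable patient at 3 × 3 on every item has a total of 11 × 9 = 99. With one frequency missing the SAP gives 10 × 9 + 3 = 93. The false change is −6 if it is missing at follow-up and +6 if at baseline. In the worst case, with all 11 frequencies missing, the total is 11 × 3 = 33 and is not set to missing.

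**TFC**

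5. Reproducing the plan's 13: with *a* three-point and *b* two-point items, *a* + *b* = 5 and 3*a* + 2*b* = 13 give only *a* = 3, *b* = 2.
6. One item missing is 1/5 = 20%, so replacement applies. Two missing is 40%, so the total is missing. With one missing, the SAP total is the observed sum × 5/4.

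| Patient | True total | Two-point item missing | Three-point item missing |
|---|---|---|---|
| All items at maximum | 13 | 11 × 5/4 = 13.75 | 10 × 5/4 = 12.5 |
| All items at half of maximum | 6.5 | 5.5 × 5/4 = 6.875 | 5 × 5/4 = 6.25 |

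7. The largest false change in a stable, fully functional patient is 13.75 − 12.5 = 1.25 points, in either direction. It needs a two-point item missing at one visit and a three-point item at the other. With one incomplete visit the score is off by +0.75 or −0.5.
8. Over the 4 × 4 × 4 × 3 = 192 patterns of the other four items when a two-point item is missing, the replacement exceeds that item's maximum in 15. The total exceeds 13 in one: the other four all at maximum.

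**Alternatives on the same examples**

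9. Replace a half-missing item by the mean of the complete items, bounded to between *s* and 4*s*. The 3 × 3 patient with one frequency missing gets 9 and a total of 99. The bounds are needed. With *s* = 4 and ten items at 0, the plain mean is 0 although 4–16 is possible; the bounded value is 4. With *s* = 1 and ten items at 9, the plain mean is 9 although 1–4 is possible; the bounded value is 4.
10. Prorate the TFC as 13 × observed sum / sum of observed maxima. At maximum, 13 × 11/11 = 13 and 13 × 10/10 = 13. At half, 13 × 5.5/11 = 6.5 and 13 × 5/10 = 6.5.

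**The case against.** The strongest case for leaving the rules alone has five parts.

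- **The half-missing rule is not always wrong.** It is exact when the observed half is 0 or the missing half is truly 1, and too high if the missing half is truly 0. Numerical anchors are printed for the PBA-s only. This stands: the rule is low whenever the missing half exceeds 1, not in every case.
- **The PBA-s is less exposed than the behavioural score.** The SAP's baseline visit lists the UHDRS but not the PBA-s, so the baseline case applies most clearly to the behavioural total. The abbreviated PBA-s has 6 of 11 items; 5/11 = 45% are missing and the total is missing under either rule. This stands.
- **The bounded rule often returns the SAP value.** It differs only when the mean of the complete items exceeds the observed half. True, but it never scores below the SAP and never leaves the possible range.
- **Proration gains little average accuracy.** Over all 576 TFC states × 5 missing items (2,880 cases, equal weights, illustrative), it is closer to the truth in 1,561, further in 1,301 and tied in 18; mean absolute error is 0.95 against 0.97. If a three-point item is truly 0 and the rest are at maximum, the true total is 10, the SAP gives 12.5 and proration 13. This stands too. The gain is a valid range and no shift for patients impaired evenly across items.
- **Protocol 8.3 rules out imputation, and SAP 4.4 opens by saying missing data will not be estimated.** Replacement sits awkwardly with both, whether by the current rules or the proposed ones. Setting incomplete totals to missing is the option that fits them.

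None of this rescues a rule that yields a TFC above 13 or hides incomplete items from the 25% limit.

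**Conclusion.** Both rules are wrong as written, and the point is minor. A half-missing behavioural or PBA-s item is understated by 50% to 75% whenever its missing half is truly 2 or more, by up to 16 − 4 = 12 points on one item, and it bypasses the 25% limit. A single missing TFC item shifts a fully functional patient by +0.75 or −0.5, with smaller shifts in patients evenly impaired across items.

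The documents give no rate of item missingness, so the effect on any summary is unknown. No test or sample size depends on these scores: SAP 6.2 treats efficacy as descriptive and exploratory, and the suicidality tables in SAP 7.8 use C-SSRS items. The conclusion assumes that 0 means absent on the UHDRS behavioural items as it does on the PBA-s. It also assumes that the scale descriptions in the supplied protocol (Amendment 05) apply to the SAP, which is based on Amendment 04 but refers to the protocol for them.

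**What to change.** Amend SAP 4.4 before database lock.

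1. **Behavioural assessment and PBA-s.** Score the item 0 if the observed half is 0. Otherwise count a half-missing item as missing. If no more than 2 of the 11 items are missing or half-missing, replace each half-missing item by the mean of the complete items, bounded between the observed half and four times the observed half. If more than 2 are incomplete, set the total to missing.
2. **TFC.** With one item missing, use 13 × observed sum / sum of the maxima of the observed items, and list the five item maxima in the SAP. Alternatively, set the TFC to missing if any item is missing; this is simpler and agrees with protocol 8.3.

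The cost is two sentences and minor programming. Some totals will become missing: a patient with three half-missing items loses a total that has eight complete items, in a study the protocol puts at 47 patients. Mean replacement still assumes that the incomplete item resembles the patient's other items.
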